## Secondary Objectives

### 1. Exploration of the pharmacodynamic effects of MAPK pathway inhibitors on pre- and on-treatment peripheral blood BRAFV600 mutational testing.

The exploration of pharmacodynamic effects will be based on the cohort of patients with advanced, BRAF-mutated disease confirmed by tissue analysis. We would expect that 50% of the cohort would have BRAF-mutated disease and that 90% of those patients will agree to participate in the pharmacodynamic studies. This results in a sample of size 50.

Our first investigation will correlate blood-assay results with pre-treatment radiographic measures of disease burden. We hypothesize that the cases with the lowest tumor burden would be most likely to have a negative blood assay result. We will use the sum of the longest diameter of tumor target lesions as the measure of disease burden using RECIST criteria (version 1.1). For this analysis, tumor burden will be a continuous outcome, and the blood assay will be classified as positive or negative. We will summarize baseline tumor burden descriptively and compare by assay result using the Wilcoxon rank-sum test. If the blood-assay is positive in 80% of the samples (N=40) and negative in 20% (N=10), a Wilcoxon-rank sum test, with a two-sided type-I error of 10%, will have 80% power to detect a difference in disease burden that is 0.95 times the common standard deviation.

The behavior of the blood-based assay with respect to early changes in disease will be assessed at the time of the first restaging. Since there are no prior data to suggest how assay levels will change in response to treatment, analyses will be primarily descriptive. Two analyses are proposed to explore the relationship between the performance of the assay and early clinical response. In both analyses, clinical response will be classified according to RECIST criteria (i.e., CR/PR vs. SD vs. PD vs. not assessable).

At the time of the first restaging, pre- and on-treatment blood-assay levels will be compared. Fold-changes in assay response will be calculated (post/pre). Fold-changes will be used as a continuous measure and will also be classified according to 0.5 or less (assay-based response), 2 or greater (assay-based progression) and between 0.5 and 2 (intermediate). Fold changes in the assay will be compared across RECIST responses using the Kruskal-Wallis test. In addition, for

assay-based response or progression, the proportions of patients with CR/PR, SD, or PD will be presented with exact 90% confidence intervals. We will further characterize the behavior of the assay by comparing assay fold changes with fold changes in tumor burden (post/pre); the relationship will be summarized graphically and using the Spearman rank correlation.

Assay performance data will also be divided into four groups defined by pre-treatment expression and at the first restaging (i.e., +/+, +/-, -/+, -/-) and compared with response. The proportions will be summarized and compared using exact confidence intervals in all four assay combinations and also in the two subgroups with a positive assay at pre-treatment.

The behavior of the blood assay over time will be summarized graphically. The status of the assay (+/-) will be shown at each assessment time for each patient. Graphics will note changes in disease status and times of disease progression and will provide an opportunity examine patient follow-up for patterns of change in the assay.

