### 1.3 Secondary Objectives

1. To explore the pharmacodynamic effects of MAPK-directed therapy on peripheral blood BRAFV600 mutation detection, we will test isolated PBL and serum from samples obtained from patients in the cohort with advanced melanoma prior to receiving treatment with MAPK-directed therapy or immunotherapy (either commercially or on protocol). Patients will have been previously identified as being positive for a BRAFV600 mutation based on the results of the testing of their tumor tissue. PBL and serum will be isolated from blood. RNA will then be isolated from tissue and PBL/serum and BRAFV600 analysis will be performed as described above. Peripheral blood samples obtained prior to each cycle of MAPK-directed therapy or immunotherapy (either every three weeks or every four weeks depending on treatment protocol) will also be tested for BRAFV600 RNA. Input RNA normalization will be carried out by using primers to a ribosomal protein, S-9, following the reverse transcription. Pre- and on-treatment BRAFV600 levels will be compared, and a blood-based response will be defined as a 50% or more decrease in signal based on acrylamide gel analysis. A blood-based progression will be defined as a doubling in signal based compared with nadir level on acrylamide gel analysis. A comparison of blood-based response or progression (  $\geq 50\%$  improvement vs.  $< 50\%$  improvement; or 100% increase vs.  $< 100\%$  increase) with clinical response (CR/PR by RECIST) and clinical progression (PD) will then be performed to assess concordance between changes over time with our assay and with imaging.

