### 5. STUDY DESIGN

#### 5.1 Sample Collection

##### Advanced Disease Cohort:

Blood samples will be obtained on participants following signed informed consent. For patients in the advanced melanoma cohort, a one-time blood sample will be obtained prior to the commencement of systemic therapy at a time when standard-of-care blood will be drawn. While it is ideal to obtain samples prior to any systemic therapy, participants who have previously received therapy, have progressed, and are in need of additional therapy will be considered suitable for participation. Participants with known BRAF mutation (determined by standard of care tissue testing) will undergo blood draws every 4 weeks (+/- 1 week) and at the time of disease progression.

**BRAF WT (tissue):** One- time, pre-treatment blood draw

**BRAF Mut (tissue):** Pre-treatment blood draw then every 4 weeks (+/- 1 week). A

blood draw at time of progression will also be obtained.

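### Section 1.3 measures blood-based progression from the nadir, but Section 9.1 classifies it only against the pre-treatment level, so no planned analysis delivers the nadir-based comparison with clinical progression

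*Combined protocol and SAP*

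**What the plan says.** All references are to the combined protocol and SAP.

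- **Section 1.3, item 1 (objective).** Response: "a blood-based response will be defined as a 50% or more decrease in signal based on acrylamide gel analysis", from a comparison of pre- and on-treatment levels. Progression: "A blood-based progression will be defined as a doubling in signal based compared with nadir level on acrylamide gel analysis". Each is dichotomised and set against clinical response (CR/PR) and clinical progression (PD), to judge whether assay and imaging agree over time.
- **Section 9.1, secondary objective 1 (analysis).** The timing is fixed first: "The behavior of the blood-based assay with respect to early changes in disease will be assessed at the time of the first restaging". Then "Fold-changes in assay response will be calculated (post/pre"), and the ratios are "classified according to 0.5 or less (assay-based response), 2 or greater (assay-based progression"), with values between 0.5 and 2 intermediate. CR/PR, SD and PD proportions within assay response and assay progression get exact 90% confidence intervals. The word nadir does not appear. The graphical summary over time shows assay status as positive or negative, not level.
- **Draw schedule.** Section 5.1 says patients with a tissue BRAF mutation "will undergo blood draws every 4 weeks (+/- 1 week) and at the time of disease progression". Section 1.3 has a draw before each cycle, "either every three weeks or every four weeks depending on treatment protocol".
- **Restaging date.** No week is given for the first restaging. Section 7 leaves response assessment to each patient's treatment protocol.

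**The concern.** One endpoint, in one cohort, set against one comparator (RECIST), has two reference levels. They coincide only when no earlier on-treatment value lies below baseline. Section 2.3 wants an assay that shows developing resistance earlier than clinical or radiographic assessment, in patients whose tumours first regress. After a fall, a doubling from nadir and a doubling from the untreated level are different events.

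Two things are at stake. First, an analyst who follows 9.1 as written will not produce the comparison of assay progression with PD that 1.3 promises, at first restaging or later. Second, with both definitions in the document and no rule between them, the choice could be made after the data are seen.

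**Working it through.** **1. Sample concerned.** 110 advanced patients × 0.50 BRAF-mutant × 0.90 participating = 49.5. This reproduces the 50 stated in 9.1. The dispute is over a definition; no sample size or power figure depends on it.

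**2. The two rules on one scale.** Set the pre-treatment level to 1. Let r be the level at restaging and m the nadir, meaning the lowest level before that draw. Section 1.3 does not say whether the nadir includes the pre-treatment value; assume it does, so m ≤ 1.

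- 9.1: response if r ≤ 0.5; intermediate if 0.5 < r < 2; progression if r ≥ 2.
- 1.3: response if r ≤ 0.5; progression if r/m ≥ 2, that is r ≥ 2m.

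**3. Where they differ.**

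| Pre | Earlier draw | Restaging | Post/pre | 9.1 label | Post/nadir | 1.3 progression? |
|---|---|---|---|---|---|---|
| 100 | 20 | 50 | 0.50 | response | 50/20 = 2.5 | yes |
| 100 | 40 | 90 | 0.90 | intermediate | 90/40 = 2.25 | yes |
| 100 | none | 40 | 0.40 | response | 40/100 = 0.40 | no |

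- A 9.1 response is also a 1.3 progression when 2m ≤ r ≤ 0.5, which requires m ≤ 0.25.
- Since m ≤ 1, r ≥ 2 implies r ≥ 2m. Every 9.1 progression is therefore a 1.3 progression, and 9.1 can only under-call.
- To reach r ≥ 2 after a fall to m, the rise from nadir must be 2/m: 4-fold at m = 0.5 and 10-fold at m = 0.2. Section 1.3 needs 2-fold.
- With no draw between baseline and restaging, m = 1 and the rules are identical (third row).
- If the nadir excluded baseline, the ordering would fail. Levels of 100, 150, 250 give post/pre 2.5 (progression) but 250/150 = 1.67 from nadir (not progression). The definition should say which is meant.

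**4. Can it happen on this schedule?** Draws are 3 to 4 weeks apart. If the first restaging is at 8 to 12 weeks (an assumption) with 4-weekly draws, one or two on-treatment draws precede it, so it can. If restaging coincides with the first on-treatment draw, it cannot.

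**5. Which analyses use the cut-off?** Only the RECIST proportions within assay response and assay progression. The Kruskal-Wallis comparison and the Spearman correlation use the continuous fold-change. The four-group analysis uses positive/negative status at two times.

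**6. Cost of a nadir reference in noise.** Assume a constant true level and independent errors with SD s on the natural-log scale. For post/pre, P(ratio ≥ 2) = 1 − Φ(ln 2 / (s√2)).

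- s = 0.3: 0.693/0.424 = 1.63, giving 5.1%.
- s = 0.2: 0.693/0.283 = 2.45, giving 0.7%.

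A doubling from the lower of two earlier values, taken at the same second on-treatment draw, has at most twice that chance (10.2% and 1.4%). Simulation gives about 9% and 1.3%. Both values of s are assumed; the documents give no assay variability.

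**The case against.** The strongest defence is one of scope. Section 1.3 speaks of change over time, while this part of 9.1 deals with early change at the first restaging. At that visit the only earlier scan is the pre-treatment one, and 9.1 also forms the tumour-burden fold-change as post/pre, so assay and imaging share a reference. Section 2.3 puts typical resistance at six to eight months (range 2 months to 2 years), so most regrowth would appear later than this visit. That is a sensible reason to keep post/pre at first restaging. It does not close the gap: the documents never state this division of scope, and if it is intended, the over-time definition in 1.3 has no analysis at all.

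Three stronger readings are tempting, and the documents do not support them.

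- *A reader might infer that 9.1 can label one patient both response and progression.* It cannot; "2 or greater (assay-based progression) and between 0.5 and 2 (intermediate") and response are mutually exclusive. The double label arises across the two sections, or within 1.3.
- *A reader might infer that the overlap within 1.3 is itself an error.* Section 1.3 sets out two separate dichotomies, one compared with CR/PR and one with PD. A patient may respond and then progress, as on imaging. A precedence rule is needed only for a single three-way classification.
- *A reader might infer that the results will be biased towards the assay missing progression.* Under-calling relative to 1.3 follows from the algebra; bias against imaging does not. A nadir rule could also call assay progression in patients with CR/PR on imaging, and 9.1 itself says there are no prior data on how levels will change.

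The doubling relative to baseline used later in 9.1 belongs to the Stage II/III cohort and settles nothing here.

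**Conclusion.** The inconsistency is real and should be resolved before analysis. Sections 1.3 and 9.1 use different reference levels for assay progression, and nothing in 9.1 carries out the nadir-based comparison with PD. Disagreement requires at least one on-treatment draw before the restaging draw. The one-directional result requires that the nadir include baseline.

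The reach is limited: a secondary, primarily descriptive analysis and one set of categorical proportions. The primary endpoint, sample size and power are untouched. How many of the roughly 50 patients would be reclassified cannot be computed from the documents, though in a group of that size a few would visibly change the proportions.

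**What to change.** Reconcile Sections 1.3 and 9.1 as follows.

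1. In 9.1, add assay-based progression as a level at least 2 times the lowest level to date, pre-treatment included. Tabulate it against RECIST PD at the first restaging and at later assessments, including the draw at progression.
2. Keep post/pre for the continuous fold-change and for assay response (0.5 or less).
3. Report post/pre of 2 or more alongside, labelled as a second definition.
4. Treat response and progression as two separate dichotomies, as in 1.3. If a single three-way classification is kept, state which label takes precedence.
5. Report the proportion of nadir doublings confirmed at the next scheduled draw, and count separately those first seen at a patient's last draw, which cannot be confirmed.

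The cost is SAP wording and some extra tables. The draws are already scheduled, so no new samples are needed. The downside is more chance doublings under a nadir reference, as sized above; item 5 makes them visible.

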Second, tumor resistance to BRAF-directed therapy typically develops within six to eight months following initial tumor regression, but with a range of 2 months to 2 years.(2, 6-9) Importantly, each described mechanism involves the retention of the initiating BRAF mutation.(10-20) As the mechanisms of resistance are just now being elucidated, we feel that diagnostic assays which may identify developing resistance at an earlier time-point than standard clinical or radiographic assessments will have the ability to assist clinicians and researchers in determining the best next treatment option for patients whose disease is progressing on BRAF-directed therapy. This is particularly important due to the fact that a number of patients treated with BRAF inhibitors progress quite quickly following initial disease regression.(7) In these patients, it is typically difficult to transition to other therapies, such as ipilimumab, due to the rapid pace of growth in these resistant tumors.(21) While there is no current data which specifically supports such a strategy, it is thought that more advanced notice of disease progression when disease growth is more modest would allow for a more timely shift in treatment and improved benefit of next line therapy. Essentially, identifying a blood-based assay that can detect more subtle changes in disease burden than standard cross-sectional imaging would be requisite towards implementing this type of an approach. In addition, earlier detection of disease progression would also predictably allow investigators to analyze tumors or circulating tumor cells in these patients with a goal of determining the specific mechanism of resistance for an individual patient. This would have the added value of predicting which next therapy would be most appropriate for any

individual patient.

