Fourth, the recommended optimal follow up of patients who are currently rendered disease free with surgery for their melanoma is unknown. Namely, the current NCCN guidelines do not recommend any blood analysis for such patients and only concede that considerations be made towards routine imaging in patients with higher risk disease (stage IIB-resected stage IV).(25) The development and validation of a blood-based prognostic biomarker would offer the potential to improve these guidelines and potential help direct radiographic imaging. As an example, it is conceivable that the positive predictive value of cross-sectional imaging would be much higher in the context of a rising biomarker, much the way it is in patients with concerning symptoms, then when imaging is performed at randomly selected intervals.

[figure not shown]
In summary, a blood-based BRAF mutational analysis has the potential to:

1. Enhance and potentially replace tissue based BRAF mutation detection.
2. Detect disease progression at an earlier time-point than imaging which may improve the effectiveness of next line therapy (given the lower tumor burden), and mechanism of resistance analysis for patients with BRAF mutant disease progressing on BRAF-directed therapy.
3. Predict which patients respond to adjuvant, BRAF-directed therapy.
4. Serve as a prognostic biomarker for patients with resected melanoma that may be followed serially and help clinicians choose which patients to perform diagnostic imaging.

Mutational testing for BRAFV600 in tumor tissue has been well described using techniques such as bidirectional direct fluorescent sequencing and allele-specific polymerase chain reaction. The sensitivity of these assays, however is limited in that the assays in current use are only able to

detect the mutation if the tumor cells constitute >5-10% of the specimen submitted for genetic analysis.(26) While this degree of sensitivity is typically sufficient to detect the presence of the BRAF mutation in a homogenous tumor nodule, this is likely not sensitive enough to detect a few tumor cells in the background of a high percentage of stromal or lymphatic elements, infiltrating lymphocytes, or peripheral blood cells.

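### Section 9.1 does not carry through the over-time comparison of assay progression with clinical progression that Section 1.3 promises for the advanced cohort

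*Combined protocol and SAP*

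**What the plan says.** Section 1.3, first secondary objective, sets two thresholds for the blood assay in the advanced cohort: a fall of at least half is a response, and a doubling relative to nadir is a progression. It says these will be compared with RECIST response and with PD "to assess concordance between changes over time with our assay and with imaging". It does not restrict the comparison to one visit, and it names no statistic.

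Section 5.1 has tissue-positive patients in this cohort bled before treatment, every 4 weeks (give or take one week), and at progression.

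Section 9.1, Secondary Objective 1, specifies:

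- Before treatment: a rank-sum comparison of baseline tumor burden by assay result.
- At the first restaging: post/pre fold-change compared across RECIST categories (Kruskal-Wallis), RECIST proportions within assay response or progression (exact 90% intervals), a Spearman correlation with change in tumor burden, and four groups formed from the pre-treatment and first-restaging results. Assay progression here is a post/pre ratio of 2 or more.
- Afterwards: "The behavior of the blood assay over time will be summarized graphically". The content of those graphs is then limited to a binary result: "The status of the assay (+/-) will be shown at each assessment time for each patient", with PD dates marked.

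Section 2.3 lists among the assay's potential uses "Detect disease progression at an earlier time-point than imaging" and states that "tumor resistance to BRAF-directed therapy typically develops within six to eight months following initial tumor regression".

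**The concern.** The 4-weekly draws and the draw at progression would let the trial describe how an assay rise relates in time to progression on imaging. Section 1.3 commits to such a comparison, and Section 2.3 explains why it is wanted. The analysis section stops at the first restaging, which is likely to come before most patients progress. It also changes the reference for assay progression from nadir to pre-treatment level, and then reduces the later data to positive or negative status.

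At stake is whether the trial will report any pre-specified number on this question. Without one, the choice of definition and summary would be made after the serial curves have been seen.

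**Working it through.** **1. The plan's own figures.** Section 9.1 gives a sample of 50 for this objective: 110 × 0.5 × 0.9 = 49.5. Its only power statement here concerns baseline tumor burden: "If the blood-assay is positive in 80% of the samples (N=40) and negative in 20% (N=10"), the test "will have 80% power to detect a difference in disease burden that is 0.95 times the common standard deviation", at two-sided 10%. Check: power = Φ(0.95 × √(ARE / (1/10 + 1/40)) − 1.645), where ARE is the efficiency of the rank-sum test relative to the t-test. This gives 0.80 with ARE 0.864 (its lower bound) and 0.84 with ARE 0.955 (normal data). Both figures reproduce, but neither bears on the serial data. No power or precision is stated for anything after the first restaging.

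**2. The two definitions side by side.** Take a pre-treatment signal of 100 that falls to a nadir of 20.

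| Later signal | Ratio to nadir (Section 1.3) | Post/pre ratio (Section 9.1) |
|---|---|---|
| 40 | 2.0: progression | 0.4: response |
| 60 | 3.0: progression | 0.6: intermediate |

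The definitions part company in the regression-then-resistance pattern that Section 2.3 describes. On the later graph, such a patient shows as positive throughout if the signal stays detectable. Marking the PD date does not help, because the assay event is not drawn.

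**3. How much falls after the last statistic.** The documents give no date for the first restaging, so 8 to 12 weeks is assumed (1.84 to 2.76 months at 4.345 weeks per month). The 6 to 8 months in Section 2.3 is treated as an exponential median from treatment start, also an assumption. Share progressed by first restaging = 1 − 0.5^(restaging time / median):

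| Median | Restaging | Progressed by then | Of 50 | Remaining |
|---|---|---|---|---|
| 6 months | 8 weeks | 0.192 | 9.6 | 40.4 |
| 6 months | 12 weeks | 0.273 | 13.7 | 36.3 |
| 8 months | 8 weeks | 0.147 | 7.4 | 42.6 |
| 8 months | 12 weeks | 0.213 | 10.6 | 39.4 |

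About 7 to 14 of 50 would have progressed by the first restaging. If all patients eventually progress under follow-up, 73% to 85% of progressions come later. Over the same 6 to 8 months (26 to 35 weeks), 4-weekly draws give 26/4 = 6.5 to 35/4 = 8.7 on-treatment samples per patient. One of these, the first-restaging sample, enters an assay-versus-RECIST calculation.

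**4. Precision of the missing estimate.** Widest exact (Clopper-Pearson) 90% interval for a proportion, over an assumed range of progressors:

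| Progressors | Interval at the widest point | Width |
|---|---|---|
| 20 | 10/20: 0.30 to 0.70 | 0.40 |
| 30 | 15/30: 0.34 to 0.66 | 0.32 |
| 40 | 20/40: 0.36 to 0.64 | 0.28 |

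For example, 24/40 = 0.60 would carry an interval of 0.46 to 0.73. The lower numbers matter because Section 1.3 includes immunotherapy patients as well as MAPK-treated ones and gives no split.

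**The case against.** The strongest reply is that this is exploratory work described as such. The numbered objective is to explore pharmacodynamic effects. Earlier detection than imaging appears only in the rationale, as a potential of the assay. Section 9.1 explains that its early-change analyses are mainly descriptive because there are no prior data on how levels move under treatment. On that view, per-patient graphs are a reasonable choice. This stands as a reason not to demand a powered test. It does not explain why a comparison written into Section 1.3 has no counterpart in Section 9.1, and a proportion or a median with an interval is itself descriptive.

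Three stronger readings are tempting, and the documents do not support them.

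- A reader might infer that assay progression is never set against imaging progression. Section 1.3 does state the comparison, and the graphs in Section 9.1 mark progression times. What is missing is a method and an estimate.
- A reader might infer that the serial samples cannot address earlier detection. Draws every 4 weeks and at progression would allow it; the gap is in the analysis text.
- A reader might infer that the first-restaging analysis will contain almost no PDs. Under the assumptions above it has about 7 to 14, which is sparse but not near-empty. The 6 to 8 months also runs from initial regression, so it describes responders, and the same sentence gives a range of 2 months to 2 years. Section 5.1 admits previously treated patients who have progressed. Early progressions could therefore be more numerous than calculated.

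**Conclusion.** The concern holds as a mismatch between Sections 1.3 and 9.1 in the advanced cohort. A nadir-based comparison over time is promised. What is specified is a post/pre comparison at the first restaging, followed by graphs of positive or negative status that cannot show a doubling in a patient who remains positive. Followed as written, the plan yields no estimate of the promised comparison, and concordance alone would not measure lead time.

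The 73% to 85% figure rests on an assumed restaging date, an assumed exponential form, the median counted from treatment start, and all patients being followed to progression. It is an order of magnitude. The textual mismatch does not depend on it.

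This is a secondary, exploratory aim and the primary objective is unaffected. It should still be corrected, because the repair is cheap and uses data already planned.

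**What to change.** In Section 9.1, Secondary Objective 1:

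1. Reconcile the two definitions of assay progression. Use the nadir-based one for all over-time analyses. For an undetectable nadir, add the rule already used for the resected cohort, where a change from non-detectable to detectable counts.
2. Plot quantitative assay levels for each patient, not only positive or negative status, with PD dates marked.
3. Report, as descriptive estimates with 90% confidence intervals: the proportion of imaging PDs preceded by assay progression; the proportion of assay progressions not followed by PD, so that false alarms over repeated draws are counted; and the median lead time (date of imaging PD minus date of first assay progression). Give these for MAPK-treated patients and, separately, for immunotherapy patients. State the expected precision over a range of progressor numbers, as above.
4. Optionally, as exploratory, fit the extended Cox model already specified for the Stage II/resected Stage III cohort, with assay progression as the time-dependent covariate for PFS.

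The cost is some SAP text and programming; no new samples or visits are needed. The limitation to state is that lead time is resolved only to the 4-week draw interval and also depends on scan schedules, which vary because Section 7 leaves response assessment to the protocol for each therapy.
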